## 0.0 Amendment Information

### 0.1 Rationale for the Amendment:

The initial protocol proposes a randomized controlled trial of rapid-start hepatitis C (HCV) treatment intervention co-located at a syringe service program. Due to the impact of the COVID-19 pandemic in New York City, enrollment in this protocol has been temporarily suspended. As New York starts to plan recovery from COVID, it is likely that elements of service delivery for people who inject drugs (PWID) will be very different. Foremost, the impact of COVID-19 on syringe service programs may limit the ability to offer co-located interventions. A recent national survey showed that 43% of programs have reduced services and nearly all had eliminated HCV and HIV testing due to the need for person-to-person contact. The prospect of an economic downturn may further limit the ability of these programs to provide health services in a tighter funding environment.

In the meantime, the need to adapt to the pandemic has rapidly increased the use of telemedicine services to engage with patients without physical contact. It is not clear whether telemedicine is equitably accessible across different patient populations. Telemedicine has been found to be acceptable for hepatitis C management in patients in several healthcare settings. Our intervention serves a unique population not covered by prior studies: they are currently injecting and recruited from the community, and so may face significant healthcare access barriers. On the other hand, they are a young population (<30 years old) that may be technologically equipped to embrace telemedicine-based HCV treatment. Understanding how to adapt existing community-based healthcare intervention for populations with limited healthcare access will be critical in the post-COVID era.

In this amendment, we will change the enrollment and analysis plans of our randomized study (called part A). This will involve conducting the analysis and reporting of comparative data between intervention and control arms, with the same study endpoints as the initial proposal. The main reason for ending enrollment at this time is the long delay we are likely to face before a co-located intervention can be offered in a physical syringe service program space. Instead, we will adapt our intervention to be telemedicine-based for continued enrollment into a nonrandomized treatment group (Part B). After the end of follow-up for part B, we will describe outcomes and compare to the previously randomized control population, to test if telemedicine-based engagement is feasible, safe, and noninferior to the co-located intervention.

### 0.2 Protocol Changes:

#### 1. Section 1.2

**Change:** Addition of: In Part B, all participants will be enrolled to the intervention group, modified to allow telemedicine delivery.

#### 2. Section 1.4: Intervention Arm

**Change:** For participants entering in Part B, the co-located rapid start intervention will be converted to telemedicine rapid-start intervention. Consented participants will have same-day or next-day telemedicine visits with a hepatitis C provider and baseline blood testing will be arranged on a personalized basis utilizing convenient community-based laboratory facilities (including current co-located SSP and commercial laboratories). For participants found to be HCV PCR positive, personal delivery or pick-up of a 28-day supply of sofosbuvir/velpatasvir (Epclusa®) will be

arranged. Telemedicine visits will be arranged two weeks after treatment delivery. For participants who confirm treatment initiation, side effects will be assessed, delivery/pick-up of the final 56-day of medication will be arranged, and week 4 monitoring labs will be offered (no longer required) and arranged.

### 3. **Section 1.7:** Secondary Objectives

**Change:** To assess the feasibility, safety, and effectiveness of a telemedicine-based rapid start intervention for hepatitis C treatment in young people who inject drugs.

### 4. **Section 3:** Study Design

**Change:** For participants entering in Part B, randomization will not occur. All participants will be assigned to the intervention arm, which we will call the telemedicine arm in this document.

**Rationale:** The part B telemedicine arm will not be randomized, and instead will be compared to previously randomized arms. This is in order to maximize sample size exposed to the intervention with the available remaining budget and grant period.

### 5. **Section 4 :** Participant Selection and Enrollment

**Change:** For participants entering in Part B, enrollment may occur in person or remotely (no person-to-person contact needed)

**Rationale:** Remote enrollment procedures will allow continued referral and enrollment even without the physical location of the syringe service program. Informed consent will be converted to electronic informed consent using a RedCAP survey, a procedure we have successfully implemented at Weill Cornell for COVID-related studies.

### 6. **Section 5.1 :** Schedule of Study Events

**Change:** Week 4 and Week 8 laboratory draws are now changed to optional, to minimize travel and physical contact. Monitoring labs for re-infection have been eliminated, and re-infection will not be analyzed for the telemedicine cohort. Instead, individuals will reach the study endpoint at either SVR 12 or at week 48, whichever comes first. The frequency of medical visits will be unchanged but physical exams will no longer be performed except as possible through telemedicine. Weekly telephone or video check-ins will also continue.

### 7. **Section 5.8:** Storage of samples for future analysis

**Change:** Storage samples collected only when feasible for Part B.

**Rationale:** Since we will now be utilizing clinical laboratories, storage of samples for research purposes will occur when feasible, but not required for all participants and all timepoints.

### 8. **Section 8.1** Sample size

**Change:** Data on the randomized controlled portion of the study (Part A) will be analyzed based on enrollment through March 1, 2020 so the power to detect a difference between the 2 groups will be reduced from what was calculated for a sample size of 54 patients..

**Rationale:** The COVID pandemic created a natural break in enrollment and inability to continue study as planned.

## 9. **Section 8:** Statistical and Analytic Considerations

**Change:** Adding the Part B analysis for comparing the telemedicine arm to the previously enrolled study arms.

**Rationale for change:** We will compare the proportion of patients who achieve SVR12 in each Part B telemedicine to (1)Part A intervention (2) Part A control, using Chi-square or Fishers' exact testing, using an intention-to-treat approach in which participants are analyzed in the group to which they are randomized. Participants with negative confirmatory HCV RNA PCR tests on study entry will not be included in the analysis, consistent with our existing approach.

## 10. **Consent form:**

The consent form was revised to reflect the addition of Part B. Part A participants do not need to be reconsented.

## 1.0 Synopsis

### 1.1 Purpose of Study:

The purpose of this randomized study is to determine whether a community-based test and treat model of hepatitis C (HCV) care delivery will be superior to the usual care practice of referral to specialist clinics for the outcomes of sustained virologic response at 12 weeks after treatment and initiation of HCV treatment for persons who inject drugs (PWID) between ages 18 and 29 who are naïve to HCV treatment

### 1.2 Design:

ST&RT is a randomized open-label clinical trial conducted in two parts. In part A, which HCV infected PWID between ages 18 and 29 will be randomized to either receive the same-day treatment initiation of the FDA-approved fixed dose combination of sofosbuvir 400mg and velpatasvir 100mg (SOF/VEL) with follow up and medical monitoring at a community site (Intervention arm) or to receive referral to an HCV treatment provider's office (Usual Care Arm). In Part B, participants will be enrolled to receive hepatitis C rapid treatment initiation in a telemedicine model.

### 1.3 Participant selection:

#### 1.3.1 Inclusion Criteria

Persons are eligible for study inclusion if they: (a) are HCV antibody positive, (b) are 18 to 29 years of age, (c) have injected drugs in the past 30 days, (d) are HCV treatment naïve, (e) are English speaking

#### 1.3.2 Exclusion Criteria

Persons excluded from the study will be (a) HIV coinfected persons (b) pregnant women, or women planning on becoming pregnant (c) participants with end-stage renal disease (d) participants with decompensated cirrhosis (c) participants on medications with treatment limiting interactions with SOF/VEL (detailed below). In part B only, participants who cannot participate in telemedicine visits (lack of telephone, smart phone or computer or internet connection) will be excluded.

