### 3.0 Study Design

This is a single-center, open-label, randomized controlled trial, in which 72 HCV antibody positive participants between ages 18-29 will be recruited in two parts. During Part A, participants will be randomized to either the rapid treatment intervention arm, or the usual care control arm. During Part B, participants will be enrolled to the telemedicine arm. Recruited individuals must have used injection drugs in the past 30 days, have no medical contraindication to sofosbuvir and velpatasvir treatment, be HIV uninfected, and be HCV treatment naïve. During part B, they must have access to technology that allows telemedicine interventions (eg telephone, smartphone, or internet connection).

The goal of the study is to provide same-day, easily accessed medical evaluation and treatment to the intervention arm. During part A, participants randomized to the intervention will receive medical evaluation, laboratory assessment including confirmatory HCV RNA testing, baseline questionnaire/interview, and distribution of a 7-day medication “starter pack” on the day of enrollment. Participants who are HCV RNA negative will be notified by phone call, be asked to return their medications but continue to be followed for research visits every 12 weeks, similar to the control-arm. During part B, participants will have the option of an in-person evaluation at the syringe service program or a telemedicine visit on the day of enrollment or the following day. They will receive community based laboratory testing at a location that is convenient to them, and participate in study interview.

During part A, HCV RNA positive participants in the intervention arm will be asked to start medications, and return to pick up an additional 21-day supply. They will receive weekly text messages during treatment to record adherence. They will receive one follow-up medical visit at 4 weeks with laboratory evaluation, with distribution of the remainder of medications, and another visit at the end of treatment. One of these two visits (the participants’ choice) will include counseling for prevention of reinfection. They will then have HCV RNA PCR testing at end of treatment and 12 weeks post treatment, and at 48 weeks to assess for reinfection. Each study visit will include a brief questionnaire and qualitative interview.

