Participants in the control arm will be provided facilitated referral to community HCV providers by an on-site care coordinator already facilitating care at the community site. HCV RNA negative participants will be called to inform them of these results, and then discontinued from the study. HCV RNA positive participants will be asked during the semi-structured interviews as at 12, 24, 36 and 48 week if they engaged in HCV treatment to assess whether their HCV referral has been filled, and to record their current HCV treatment status. They will also receive repeat HCV RNA testing at week 12, 24, and 48. Participants that have started treatment will be asked to sign consent for release of medical records pertaining to HCV-related laboratory testing to determine achievement of treatment response.

During part B, HCV RNA positive participants will have a 28-day supply of medications delivered, or available for pickup, as they prefer. The schedule of visits will be similar except that laboratory testing at week 4 will be optional, and all visits will be offered through telemedicine.

The three arms will be compared for the main outcome of SVR12 using a modified intention to treat analysis in which participants will be analyzed in the group they are randomized except for those who are (a) discontinued due to HCV RNA negative status or (b) found to have previously undiagnosed HIV at enrollment. Secondary outcomes will be compared using the same modified intention to treat design.

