## 8.3 Data Analysis

### 8.3.1 Analysis of clinical outcomes data

For the primary analysis, after the completion of part A, we will compare the proportion of patients who achieve SVR12 in each arm using Chi-square or Fishers’ exact testing, using an intention-to-treat approach in which participants are analyzed in the group to which they are randomized. Participants with negative confirmatory HCV RNA PCR tests on study entry will not be included in the analysis.

For secondary analyses, we will:

- Compare the proportion of patients who achieve end-of-treatment response using Chi-square or Fishers’ exact testing
- Compare the proportion of patients who complete treatment, using Chi-square or Fishers’ exact testing
- Compare the proportion of patients who have HCV reinfection, using Chi-square or Fishers’ exact testing
- Describe adherence for participants in the Intervention arm only
- Describe demographic, clinical and behavioral factors for participants who have HCV reinfection or incident HCV infection

We will also perform the same analyses using an “as-treated” approach, in which participants in the intervention arm will not be included if they failed to initiate HCV treatment, or discontinued treatment for reasons clearly unrelated to the treatment intervention (e.g. relocation, incarceration).

After the completion of part B, we will compare the proportion of patients who achieve SVR12 in each Part B telemedicine to (1)Part A intervention (2) Part A control, using Chi-square or Fishers’ exact testing, using an intention-to-treat approach in which participants are analyzed in the group to which they are randomized. Participants with negative confirmatory HCV RNA PCR tests on study entry will not be included in the analysis.

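### The non-randomised Part B telemedicine arm is tested without adjustment against the Part A arms under a randomised intention-to-treat rule, so a difference in SVR12, or its absence, cannot be credited to telemedicine

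*Combined protocol and SAP*

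**What the plan says.** **Entry.** Section 1.3.2 states: "In part B only, participants who cannot participate in telemedicine visits (lack of telephone, smart phone or computer or internet connection) will be excluded". Section 3.0 repeats the rule: "During part B, they must have access to technology that allows telemedicine interventions (eg telephone, smartphone, or internet connection". No Part A criterion in sections 1.3.1, 1.3.2 or 3.0 corresponds to it.

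**Allocation.** Item 4 of section 0.2 states: "The part B telemedicine arm will not be randomized, and instead will be compared to previously randomized arms".

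**Analysis.** Section 8.3.1 states that after Part B "we will compare the proportion of patients who achieve SVR12 in each Part B telemedicine to (1)Part A intervention (2) Part A control". The tests are Chi-square or Fisher's exact, and the approach is called intention-to-treat, with people analysed by the arm they were randomised to. Item 9 of section 0.2 has the same wording. Section 3.0 says "The three arms will be compared for the main outcome of SVR12" and applies a modified intention-to-treat rule, again by randomised group. None of these places gives covariate adjustment, restriction, a sensitivity analysis or a caveat for Part B.

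**Purpose.** Section 0.1 says the comparison is "to test if telemedicine-based engagement is feasible, safe, and noninferior to the co-located intervention". No margin is given. Item 8 in section 1.7 lists effectiveness of the telemedicine model among the secondary outcomes.

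**The concern.** An intention-to-treat analysis protects a comparison because randomisation made the groups alike at entry. Part B participants were not randomised, so the rule does not define their analysis set, and naming it lends the comparison a protection it lacks.

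The two parts differ in who enters and when: the access rule, remote enrolment in place of physical referral to the syringe service program, and a later period of service delivery. They also differ in monitoring. A crude test cannot separate these from the effect of telemedicine.

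At stake is the conclusion for item 8. If people with access do better, the filter would favour Part B over Part A control and could mask a loss relative to the co-located intervention. The amendment itself raises the question of access: "It is not clear whether telemedicine is equitably accessible across different patient populations". A non-significant Chi-square result against the Part A intervention arm could also be taken as noninferiority, which that test does not show.

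**Working it through.** **1. The cohorts side by side**

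| Feature | Part A | Part B | Where |
|---|---|---|---|
| Allocation | Randomised 1:1 | All to telemedicine | 8.2; 0.2 item 4 |
| Access rule | None | Required | 1.3.2; 3.0 |
| Enrolment route | Physical referral to the syringe service program | Remote permitted | 1.4.1 |
| Calendar period | Through March 1, 2020 | Later | 0.2 item 8; 8.1 |
| Week 4 laboratory draw | Scheduled (intervention arm) | Optional | 0.2 item 6; 5.1; 5.2 |

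The last row can be seen as part of the telemedicine package. The rows on access, route and period concern who was enrolled and when, and these confound the comparison.

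**2. The plan's own figure**

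Section 8.1 gives 80% power for 41% versus 78% with 27 per arm at alpha 0.05, taken here as two-sided. With pooled variance, the null standard error is √(2 × 0.595 × 0.405/27) = 0.1336 and the alternative standard error is √((0.41 × 0.59 + 0.78 × 0.22)/27) = 0.1238. Power = Φ((0.37 − 1.96 × 0.1336)/0.1238) = 80.9%. Exact enumeration gives 80.2% for Chi-square and 72.1% for Fisher. The stated figure is reproduced for Part A. The documents give no sample size, power or margin for Part B.

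**3. Possible size of the access filter**

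Let f be the share of Part A that would fail the Part B rule, and g the SVR12 gap between people with and without access. If p is the rate among those with access, Part A shows p − f × g, and Part B shows p when telemedicine has no effect. The apparent difference is f × g. The documents give neither f nor g, so these values are assumed:

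- f = 0: 0 points for any g
- f = 5%, g = 10 points: 0.5 points
- f = 25%, g = 20 points: 5 points
- f = 30%, g = 40 points: 12 points

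**4. What such a bias would do**

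The next table assumes 27 per group and no effect of telemedicine in the middle two columns, which come from exact enumeration of the Chi-square test. The last column is Φ(b/SE − 1.96), where b is the bias, m the margin, the Part B rate is 0.78 − m + b, and SE is the unpooled standard error. Margins of 10 to 20 points are assumed.

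| Bias (points) | Significant for Part B, Part A at 78% | Significant for Part B, Part A at 41% | False noninferiority against 78% |
|---|---|---|---|
| 0 | 2.9% | 2.3% | 2.5% |
| 2 | 4.2% | 3.2% | 3.6–3.7% |
| 4 | 6.2% | 4.3% | 5.1–5.3% |
| 8 | 12.5% | 7.5% | 9.7–10.4% |
| 12 | 23.9% | 12.5% | 17.1–19.0% |

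**5. Precision**

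At 78% in both groups of 27, the 95% half-width for a difference is 1.96 × √(2 × 0.78 × 0.22/27) = 22 points. Part A was cut short, so the real interval against it may be wider.

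**The case against.** The strongest reply is that the access rule excludes almost nobody. Section 3.0 lists a telephone as one example of adequate technology, and section 1.4.2 allows evaluation by telephone, by video or in person. Part A also assumed a phone: weekly texts in the intervention arm (1.4.2, 5.3), monthly calls in usual care (1.4.3), and RNA-negative results given by telephone (3.0). Section 0.1 adds that this young population may be well equipped for telemedicine. This stands. Phone contact was a Part A procedure rather than an entry condition, and no section says access was recorded, but f may well be close to zero.

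The direction is also open. Part A had its own filter in physical referral, and section 2.1 notes that suburban, housed young people who inject drugs make less use of harm reduction services. Part B may therefore reach people whom Part A missed.

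A reader might infer that the access filter makes telemedicine look better than it is. The documents do not support that: they fix neither the size nor the sign of the net bias.

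A reader might also infer that Part B is passed off as randomised. Sections 0.1 and 0.2 say plainly that it is not, and the comparison serves a secondary outcome in a self-described pilot. The intention-to-treat phrase may be carried over from the Part A analysis. It still stands in the analysis section and in section 3.0, and it leaves the Part B analysis set undefined.

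**Conclusion.** The concern holds for the Part B comparisons only. The intention-to-treat rule cannot apply to participants who were never randomised, and this needs no assumption. Nor can an unadjusted test against earlier arms attribute a difference in SVR12, or its absence, to telemedicine while entry rule, enrolment route and period all differ.

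The access filter is one contributor. Its size runs from 0 to 12 points under assumed values (0 to 30% of Part A without access, an SVR12 gap of up to 40 points in favour of those with access). The upper end needs both assumptions at their extremes, and the lower end is plausible on the documents. Even 12 points is well below the 37-point contrast planned for Part A (78% − 41%), so the filter alone would not produce an apparent effect of that size.

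It might seem to follow that restricting Part A to people with access would repair the comparison. It would not, because every other difference between the cohorts would remain. The randomised Part A primary analysis is untouched.

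**What to change.** In section 8.3.1, item 9 of section 0.2 and section 3.0:

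1. Remove the randomised intention-to-treat wording for Part B and define its analysis set as all enrolled HCV RNA positive participants. Section 3.0 also excludes previously undiagnosed HIV; say whether that holds for Part B.
2. Label both Part B comparisons non-randomised.
3. Report SVR12 differences with confidence intervals, beside a table of Part A and Part B baseline characteristics. Do not present the p-values as evidence of a causal telemedicine effect or of noninferiority.
4. Limit the conclusion for item 8 of section 1.7 to people with telemedicine access.
5. Where Part A access can be recovered from contact records, add a sensitivity analysis restricted to Part A participants who would have met the Part B rule. Keep the comparison with all Part A participants as the main one. If access proves near-universal, say so; that settles this part of the concern.

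The cost is wording, one baseline table and a small chart check. The downside is a more cautious conclusion about telemedicine.

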### 1.4 Study procedures

#### 1.4.1 Enrollment and sampling

Potential research participants will be recruited by referral from an ongoing NIH funded study aiming at preventing HCV among young current injectors (R01DA041501), hereafter referred to as the parent

study. The parent study will conduct a randomized, controlled trial to assess the effectiveness of a “Staying Safe” prevention intervention in reducing injection-related risk behavior and HCV incidence among 18-29 year-olds who inject opioids (heroin and/or POs) and test HCV and HIV antibody-negative at screening. The parent study is continuing to enroll participants and perform HCV testing. Whereas previous procedures would have required that the participant be referred physically to the syringe service program, we are now allowing for remote enrollment by phone or video as the first point of contact. Since the parent study is still operating, we expect to continue to receive referrals of HCV-infected people. Candidates for the parent study who test HCV antibody positive at the screening visit, will be immediately offered enrollment in ST&RT. The target sample size of 27 participants per arm is selected to show a hypothesized difference in SVR12 rates of about 35% with 80% power at a level of 0.05. Participants who are enrolled but negative on confirmatory testing (an expected 25% of participants) will be replaced. These participants will not receive treatment interventions but continue to be followed for monitoring of HCV re-infection incidence. We anticipate enrolling 36 participants per arm to achieve the target of 27 confirmed infections per arm.

